#### 9.1.3.4 Sample Shipment

Slides should be hand delivered (Dana-Farber sites) or couriered (MGH sites) to:

Sample shipment must include a copy of the Tissue Biomarker Worksheet (Appendix C) and a redacted copy of the pathology report with patient's study ID number in place of identifiers. Please retain a copy of the worksheet at the site and also send a copy of the worksheet to the Study Coordinator at Dana-Farber.

#### 9.1.3.5 Description of Assay

Next generation sequencing approaches to assess *CDKN2A*, *STAG2*, *TP53*, and other aberrations will be used. Immunohistochemistry for IGF-1R, insulin receptor, and ErbB3 will be performed. This work will be performed at Dana-Farber.

RNA-Seq will also be performed where applicable to evaluate gene expression. This work will be performed by NantOmics (ImmunityBio).

### 9.2 Banking for Potential Future Research

For patients who provide additional consent for banking, remaining tumor material, PBMCs, blood, extracted nucleic acids will be stored for up to 5 years after the completion of the trial for potential future correlative biology studies and correlation with clinical data. Future research may be performed at the Dana-Farber Cancer Institute or with outside collaborating Investigators. If samples and data are shared with outside collaborators the information will be processed in a deidentified manner.

### **9.3 Summary of Blood Volumes for Research Blood Draws**

Cohort A:

The volume needed for the required correlative biology draws is 45 mL in Cycle 1, 25 mL in Cycle 2, 20 mL in Cycle 3, and 5 ml in Cycle 4. Subsequently, 20 ml of blood will be drawn at the start of cycle 5, 7, 9 and 11, and at time of progression or other reason for off protocol therapy. Assuming a 40 kg patient enrolls, 45 mL will represent 1.5% of that patient's estimated blood volume of 3000 mL.

Cohort B:

The volume needed for the required correlative biology draws is 35 mL in Cycle 1, 15 mL in Cycle 2, 10 mL in Cycle 3, and 5 ml in Cycle 4. Subsequently, 10 ml of blood will be drawn at the start of cycle 5, 7, 9 and 11, and at time of progression or other reason for off protocol therapy. Assuming a 40 kg patient enrolls, 35 mL will represent 1% of that patient's estimated blood volume of 3000 mL.

If a treating site or investigator has concerns about this volume of blood for a specific patient, prioritize the serum separator tube, followed by the CellSave tube then lastly the EDTA tube.

## 10 STUDY CALENDAR

Baseline laboratory tests and ECG must be completed within 14 days prior to the date of enrollment. Laboratory tests used to meet eligibility requirements may be completed within 14 days prior to date of enrollment, but select tests must be repeated prior to Cycle 1, Day 1 if obtained  $> 5$  days prior to Cycle 1, Day 1 as described in section 5.2. Baseline disease assessments, such as MRIs, CT scans and nuclear medicine studies, must be performed within 28 days prior to the date of enrollment.

Once enrolled, required observations should be obtained within  $\pm 3$  days of the protocol-specified date, unless otherwise noted. Start of subsequent cycles may be  $+/- 3$  days from day 29 of the previous cycle.

Observation	Screening	Cycle 1 	Cycle 2	Subsequent Cycles	End of Therapy 	Follow-up 
Physical Exam  (Includes Ht, Wt, BSA, Vital signs  ; Performance status  only during screening)	X	Weekly	Start of cycle and day 15	Start of cycle and day 15	X	X 
CBC, Diff, Platelets 	X	Twice weekly 	Start of cycle and weekly 	Start of cycle and day 15 	X	X 
Electrolytes, Calcium, Magnesium, Phosphorus, BUN, Serum Creatinine, Glucose 	X	Weekly	Start of cycle and day 15 	Start of cycle and day 15 	X	X 
AST, ALT, Alk Phos, Total + Direct Bilirubin, Albumin 	X	Weekly	Start of cycle and day 15 	Start of cycle and day 15 	X	X 
Serum or urine pregnancy test 	X		Start of cycle	Start of cycle		
ECG	X					
Disease evaluation 	X		X 	X 	X 	X 
Blood for pharmacodynamic markers and ctDNA		See Section 9.1	See Section 9.1	See Section 9.1	See Section 9.1	
Tissue for biomarker studies	See Section 9.1				See Section 9.1	

### OBTAINT OTHER STUDIES AS NEEDED FOR GOOD PATIENT CARE.

1. Laboratory studies obtained in screening do not need to be repeated on Cycle 1, Day 1, UNLESS obtained  $> 5$  days prior to Cycle 1 Day 1. In that event repeat the following: CBC; creatinine or creatinine clearance; bilirubin; ALT; albumin; fasting glucose or random glucose.
2. End of therapy visit and observations should be performed within 7 days of decision to permanently discontinue palbociclib and ganitumab ( $\pm 7$  days).
3. All participants will have a follow-up visit approximately 30-days following their last dose of study therapy. days or until all toxicity related to the study drug has resolved, whichever is longer. For participants who are unable to return to the study center, observations may be performed at referring center.
4. Vital signs include temperature, heart rate, blood pressure, respiratory rate, and oxygen saturation.

5. Required for verification of eligibility. Creatinine clearance may be required at screening if creatinine does not meet criteria in Section 3.1.6.3.
6. More frequent CBCs and chemistries may be needed as part of good patient care, particularly if adverse events noted during more frequent lab screenings during Cycles 1 and 2.
7. Obtain for females 12 years of age and older or post-pubertal.
8. Studies obtained as part of disease evaluation will depend upon underlying sites of disease and initial imaging modalities. Studies may include anatomic imaging, nuclear imaging, bone marrow biopsies. Baseline disease status tests must be performed  $\leq$  28 days prior to study registration and subsequent to any intervening therapy.
9. Perform disease re-staging during Week 3 or 4 of Cycles 2, 4, 6, 8, 10 and 12. Confirmatory scans will also be obtained 4 weeks following initial documentation of an objective response (partial response or better).
10. Once a participant is off protocol therapy, they will be followed for survival until one year after the last dose of protocol therapy is given to the last enrolled patient. Participants will undergo disease surveillance at the discretion of their local treating physician following completion of study therapy.

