### 1.3 Secondary Objective

1.3.1 To estimate progression-free survival and overall survival in patients with relapsed or refractory Ewing sarcoma as well as in the separate cohort of patients with SDH-deficient GIST treated with the combination of palbociclib and ganitumab.

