## 2.4 Rationale for evaluation of palbociclib and ganitumab in SDH-Deficient GIST

GIST is among the most common soft tissue sarcomas, with an estimated annual incidence in the US of 6,000 cases. While activating mutations in the receptor tyrosine kinase *KIT* represent the most common oncogenic driver in this disease, 10-15% of cases are characterized by loss of the succinate dehydrogenase (SDH) complex, leading to altered metabolism and epigenetic dysregulation. Patients with metastatic or unresectable SDH-deficient GIST are treated with tyrosine kinase inhibitors as standard therapy, though response rates are modest and more targeted therapies are urgently needed.

Prospective trials studying effects of treatment in SDH-deficient GIST are limited. As compared to imatinib, sunitinib demonstrated activity in a cohort of 7 patients, with one patient achieving a partial response. In a study of regorafenib which included 6 SDH-deficient GIST patients, two of these patients experienced a PR, with a median PFS of 10 months. In a recent study of linsitinib in SDH-deficient GIST, no responses were seen, and median PFS was 10 months.

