### 5.7 Duration of Follow Up

Participants will return to the study center for adverse event follow-up approximately 30 days from last dose of protocol therapy. This period may be extended until resolution of any ongoing adverse events. Participants removed from protocol therapy for unacceptable adverse event(s) will be followed until resolution or stabilization of the adverse event. For participants unable to return to the study center for the planned 30-day follow-up visit, documentation of a clinic evaluation at their referring center is acceptable.

Patients will be followed for survival until 1 year from when the last dose of protocol therapy is given to the last enrolled participant. Return to the study center will not be required as part of survival follow-up.

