#### 12.1.2 Timelines for Data Submission

All investigative sites are expected to submit data in InForm according to the following timelines.

Form	Submission Timeline
Eligibility Checklist	Complete prior to registration
On Study Form	Within 14 days of registration
Toxicity Log (Baseline Adverse events)	Within 14 days of registration
Baseline Disease Assessment Form	Within 14 days of registration
Reporting Period Forms	Cycle 1: Within 5 business days of the last day of the cycle Other Cycles: Within 10 days of the last day of the cycle
Toxicity Log	Cycle 1: Within 5 business days of the last day of the cycle Other Cycles: Within 10 days of the last day of the cycle
Response Assessment Form	Within 14 days of the completion of disease evaluation
Off Protocol Therapy Form	Within 14 days of completing treatment
Follow-up Form	Within 14 days of the protocol defined follow up visit date and every 3 months once off therapy until 1 year after the last enrolled patient receives their final dose of protocol therapy
Off Study Form	Within 14 days of being taken off study for any reason
Outcome Form	Within 14 days of being taken off study for any reason

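### No progression assessment or progression data are required after protocol therapy, and the two PFS censoring rules conflict, so PFS beyond end of therapy is open to ascertainment bias

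*Combined protocol and SAP*

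**What the plan says.** Section 1.3 sets the objective: "To estimate progression-free survival and overall survival in patients with relapsed or refractory Ewing sarcoma", and likewise for the SDH-deficient GIST cohort.

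On treatment, Section 10 footnote 9 gives the schedule: "Perform disease re-staging during Week 3 or 4 of Cycles 2, 4, 6, 8, 10 and 12". The calendar adds an end-of-therapy evaluation.

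After treatment, footnote 10 says of participants that "they will be followed for survival until one year after the last dose of protocol therapy is given to the last enrolled patient", and then: "Participants will undergo disease surveillance at the discretion of their local treating physician following completion of study therapy". Section 5.7 agrees on the purpose of this follow-up and adds: "Return to the study center will not be required as part of survival follow-up". Section 12.1.2 has a Follow-up Form due "every 3 months once off therapy until 1 year after the last enrolled patient receives their final dose of protocol therapy", but does not list its contents.

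PFS is defined twice. Section 11.1 counts death from any cause and censors at the last disease evaluation. Section 13.5 counts only deaths from disease and censors at last follow-up.

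Section 2.4 gives a 10-month median PFS for SDH-deficient GIST in two earlier studies. In the linsitinib study, "no responses were seen, and median PFS was 10 months"; the regorafenib study reports the same median.

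**The concern.** A patient can stop protocol therapy without progression by reaching 12 cycles, by toxicity or failure to resume within 21 days (Section 6.1), or by withdrawal (Section 5.6). From then on, whether and when progression is found depends on unscheduled local scans, and the protocol does not say that their results reach the study database.

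The conflict over censoring makes this worse. If contact continues for survival only and Section 13.5 is followed as written, months without any scan count as progression-free. Section 11.1 avoids most of that, but the two sections would give different curves from the same data.

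Two other planned results use the same dates: duration of response (Section 11.1), which needs objectively documented progression, and the log-rank test of ctDNA positivity against PFS (Section 13.6).

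**Working it through.** The plan states no sample size, precision or power for PFS, so there is no planned figure to reproduce.

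**Step 1: when scheduled scanning ends.** The cap is 12 cycles of 28 days (Section 5.1.1). 12 × 28 = 336 days; 336 / 30.4375 = 11.04 months. The Cycle 12 scan window (Week 3 or 4) is days 323 to 336 without delays.

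**Step 2: share progression-free at the cap.** Assume exponential PFS with median M: S = 0.5^(11.04/M).
- M = 10 (Section 2.4): 0.5^1.104 = 0.465; × 12 = 5.6 patients in Cohort B.
- M = 6: 0.279. M = 14: 0.579.
- The readable text gives no median PFS for Ewing sarcoma. At assumed medians of 2 to 6 months the share is 0.022 to 0.279, or 0.3 to 4.2 of 15.

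**Step 3: can the median be read on treatment?** The binomial chance that at least 6 of 12 have progressed by the cap, each with probability 1 − S, is 70% at a true median of 10 months, 53% at 12, 33% at 15 and 15% at 20.

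**Step 4: size of the bias.** Kaplan-Meier estimates from 400,000 simulated patients. All settings are assumptions: exponential PFS with a 10-month median, exponential post-progression survival with median 12 or 24 months, 8-weekly scans to the cap, survival follow-up of 24 to 42 months, and 0% or 15% stopping early without progression. All simulated deaths follow progression, so they count under both definitions.

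| Reading | PFS at 18 months | PFS at 24 months |
|---|---|---|
| True value | 0.29 | 0.19 |
| 8-weekly scans continued after therapy | 0.32 | 0.19 |
| Local scans every 3 or 6 months, reported | 0.31 | 0.20 to 0.21 |
| No post-therapy scans, Section 11.1 | 0.38 to 0.39 | 0.23 to 0.25 |
| No post-therapy scans, Section 13.5 | 0.43 to 0.47 | 0.37 to 0.44 |

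The estimated median is 11.0 months in every row. The gap from 10 comes from the 8-week scan interval, not from follow-up after therapy.

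With a true median of 15 months, the estimated median is 16.6 with continued 8-weekly scans, 17.0 with reported local scans, 17.7 to 18.7 under Section 11.1 and 25 to 33 under Section 13.5. Under Section 11.1 the 24-month error can then go either way: 0.31 to 0.34 against a true 0.33.

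**Step 5: early stopping.** With a 10-month median, 15% early stopping and no local scans, 11-month PFS moves from 0.465 to 0.49 to 0.50 under Section 13.5, and to 0.47 to 0.48 under Section 11.1.

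**The case against.** The strongest reply is that follow-up for progression does not clearly end with treatment. The calendar marks disease evaluation in the follow-up column. Section 11 opens by referring to required staging during follow-up. The note under the overall response table asks for efforts to document progression after discontinuation. A form is due every 3 months and may already capture progression and new therapy.

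This stands in part: a reader might infer that progression is no longer followed once treatment stops, and the documents do not go that far. But the calendar mark carries footnote 10, Section 11 points back to that calendar, the note concerns symptomatic deterioration, and the form's fields are not given. None of these sets an interval or requires the dates.

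A reader might also infer that PFS cannot be estimated without bias, or cannot be set beside the 10-month figures in Section 2.4. That is too strong. A 10-month median lies inside the 11.04-month scheduled window, reported local scans bring the late curve close to the truth, and Section 13.5 plans no comparison with the earlier studies. Nor is the 47% a measure of bias: it is the share leaving scheduled scans at the cap.

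Finally, PFS here is descriptive and secondary, in cohorts of 15 and 12 evaluable patients. That limits the importance of the point without removing it.

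**Conclusion.** The point holds in a limited form. After therapy the plan sets no disease-assessment schedule and requires no progression or new-therapy dates, while its two PFS definitions censor differently. PFS beyond end of therapy is therefore open to ascertainment bias. In the illustration the bias is large and upward if Section 13.5 is applied without post-therapy scans (0.37 to 0.44 against 0.19 at 24 months) and modest under Section 11.1 (0.23 to 0.25).

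The patients exposed are those who stop without progression: about 47% of Cohort B at the cap if PFS is exponential with a 10-month median, and fewer in Cohort A if its median is shorter. The simulated sizes depend on the assumed survival and follow-up times. A median near 10 months remains estimable on treatment; a clearly longer one may not be. The primary response endpoint is unaffected, and no figure stated in the plan is wrong on this point.

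**What to change.** 1. In Section 5.7 and Section 10 footnote 10, state that patients who stop without progression are followed for progression as well as survival.
2. On the existing 3-monthly Follow-up Form, record the date and result of each usual-care surveillance scan, the progression date and the start date of any new anti-cancer therapy, if these are not already captured.
3. Use one PFS definition in Sections 11.1 and 13.5. It should censor at the last actual disease evaluation, not last contact, settle which deaths count, and state how new therapy is handled.
4. Place any headline landmark before the Cycle 12 scan window, for example 6 and 9 months. An 11-month landmark (11 × 30.4375 = day 335) falls inside that window, so many patients would already be censored. Nine months (day 274) falls inside the Cycle 10 window (days 267 to 280), which blurs it slightly, but patients still on treatment remain under scheduled assessment.
5. Label later PFS as based on unscheduled local scans.

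The cost is minor data entry, with no added imaging. Post-therapy scan intervals will still be irregular, and the late PFS curve may be shorter or slightly less favourable.

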## 11 MEASUREMENT OF EFFECT

The primary endpoint of the study will be assessed by the below criteria. See Section 10 for required disease staging at study entry, after initiation of protocol therapy and during follow-up. Confirmatory scans will also be obtained a minimum of 4 weeks following initial documentation of an objective response.

### 11.1 Key Definitions

Duration of overall response: The duration of overall response is measured from the time measurement criteria are met for CR or PR (whichever is first recorded) until the first date that recurrent or progressive disease is objectively documented (taking as reference for progressive disease the smallest measurements recorded since the treatment started, or death due to any cause. Participants without events reported are censored at the last disease evaluation).

Duration of overall complete response: The duration of overall CR is measured from the time measurement criteria are first met for CR until the first date that progressive disease is objectively documented, or death due to any cause. Participants without events reported are censored at the last disease evaluation.

Duration of stable disease: Stable disease is measured from the start of the treatment until the criteria for progression are met, taking as reference the smallest measurements recorded since the treatment started, including the baseline measurements.

Progression-Free Survival: Progression-Free Survival (PFS) is defined as the time from registration to the earliest time of progression or death due to any cause. Participants alive without disease progression are censored at date of last disease evaluation.

Overall Survival: Overall Survival (OS) is defined as the time from registration to death. Participants alive are censored at date of last follow-up.

### 11.2 Antitumor Effect

Response and progression will be evaluated using Response Evaluation Criteria in Solid Tumors (RECIST) guideline (version 1.1). Changes in the largest diameter (unidimensional measurement) of the tumor lesions and the shortest diameter in the case of malignant lymph nodes are used in the RECIST criteria.

#### 11.2.1 Definitions

Measurable disease: For lesions other than lymph nodes, measurable lesions are defined as those that can be accurately measured in at least one dimension (longest diameter to be recorded) as  $\geq 20$  mm by chest x-ray or  $\geq 10$  mm with CT scan, MRI, or calipers by clinical exam. All tumor measurements must be recorded in millimeters (or decimal fractions of centimeters).

For malignant lymph nodes to be considered pathologically enlarged and measurable, a lymph node must be  $\geq 15$  mm in short axis when assessed by CT scan (CT scan slice thickness recommended to be no greater than 5 mm). At baseline and in follow-up, only the short axis will be measured and followed.

**Non-measurable evaluable disease:** All other lesions (or sites of disease), including small lesions (longest diameter  $<10$  mm or pathological lymph nodes with  $\geq 10$  to  $<15$  mm short axis), are considered non-measurable disease. Leptomeningeal disease, ascites, pleural/pericardial effusions, lymphangitis cutis/pneumonitis, inflammatory breast disease, and cystic lesions are all considered non-measurable (except as described in Section 11.3.1.3). Bone lesions are considered non-measurable unless associated with a soft tissue lesion that itself meets criteria for measurable disease.

**Important notes:** Tumor lesions that are situated in a previously irradiated area are not considered measurable or evaluable unless that site meets criteria for progression after completion of radiation.

Cystic lesions that meet the criteria for radiographically defined simple cysts should not be considered as malignant lesions (neither measurable nor non-measurable) unless biopsy proven since they are, by definition, simple cysts.

‘Cystic lesions’ thought to represent cystic metastases, particularly if biopsy proven, can be considered as measurable lesions, if they meet the definition of measurability described above. However, if non-cystic lesions are present in the same participant, these are preferred for selection as target lesions.

### 11.2.2 Requirements for Disease Assessments

Investigators are to determine the optimal mode of disease assessment at baseline, including anatomic imaging studies, nuclear medicine studies, clinical measurements, tumor markers, and bone marrow biopsies. The same method of assessment and the same technique should be used to characterize each identified and reported lesion at baseline and during follow-up. Imaging-based evaluation is preferred to evaluation by clinical examination unless the lesion(s) being followed cannot be imaged but are assessable by clinical exam.

All measurements should be taken and recorded in metric notation using a ruler, calipers, or a digital measurement tool. All baseline evaluations should be performed as closely as possible to the beginning of treatment and never more than 28 days before enrollment.

### 11.2.3 Response Criteria

#### 11.2.3.1 Evaluation of Target Lesions

**Target lesions:** All measurable lesions up to a maximum of 2 lesions per organ and 5 lesions in total, representative of all involved organs, should be identified as **target lesions** and recorded and measured at baseline. Target lesions should

be selected on the basis of their size (lesions with the longest diameter), be representative of all involved organs, but in addition should be those that lend themselves to reproducible repeated measurements. It may be the case that, on occasion, the largest lesion does not lend itself to reproducible measurement in which circumstance the next largest lesion which can be measured reproducibly should be selected. A sum of the diameters (longest for non-nodal lesions, short axis for nodal lesions) for all target lesions will be calculated and reported as the baseline sum diameters. If lymph nodes are to be included in the sum, then only the short axis is added into the sum. The baseline sum diameters will be used as reference to further characterize any objective tumor regression in the measurable dimension of the disease.

Complete Response (CR): Disappearance of all target lesions. Any pathological lymph nodes (whether target or non-target) must have reduction in short axis to <10 mm.

Partial Response (PR): At least a 30% decrease in the sum of the diameters of target lesions, taking as reference the baseline sum diameters.

Progressive Disease (PD): At least a 20% increase in the sum of the diameters of target lesions, taking as reference the smallest sum on study (this includes the baseline sum if that is the smallest on study). In addition to the relative increase of 20%, the sum must also demonstrate an absolute increase of at least 5 mm. (Note: the appearance of one or more new lesions is also considered progressions).

Stable Disease (SD): Neither sufficient shrinkage to qualify for PR nor sufficient increase to qualify for PD, taking as reference the smallest sum diameters while on study.

